9.6. Safety Analysis

Summaries and analyses of the primary safety endpoint will be based on the per protocol analysis set. Summaries and analyses of all other safety parameters will include all patients in the Safety Analysis Set.

9.6.1. Analysis of Primary Endpoint

Dose-Limiting Toxicity (DLT) is the primary endpoint of the dose escalation component of the study. The occurrence of DLTs observed in the dose level cohorts is used to estimate the MTD as described in Study Design [Section 3](#). AEs constituting DLTs will be listed by dose level.

9.6.2. Analysis of Secondary Safety Endpoints

9.6.2.1. Adverse Events

AEs will be graded by the investigator according to the Common Terminology Criteria for Adverse Events (CTCAE) version 4.03 and coded using the Medical Dictionary for Regulatory Activities (MedDRA). The focus of AE summaries will be on Treatment Emergent Adverse Events, those with initial onset or increasing in severity after the first dose of study medication. The number and percentage of patients who experienced any AE, SAE, treatment related AE, and treatment related SAE will be summarized according to worst toxicity grades. The summaries will present AEs both on the entire study period and by cycle (Cycle 1 and Cycles >2).

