2.2. Endpoints

Primary Endpoint

- First 2 cycles Dose-Limiting Toxicity (DLT) of PF-05082566 in combination with MK-3475.

Secondary Endpoints

- Adverse events as characterized by type, frequency, severity (as graded by NCI CTCAE v.4.03), timing, seriousness and relationship to study therapy PF-05082566 in combination with MK-3475;

- Laboratory abnormalities as characterized by type, frequency, severity (as graded by NCI CTCAE v.4.03);
- Vital signs, weight, ECOG Performance Status;
- PK parameters of PF-05082566 and MK-3475, including but not limited to C_{max} , C_{trough} , T_{max} , AUC_{0-last} , $AUC_{0-\infty}$, CL and Vd (as data permits);
- Anti-Drug Antibody levels for PF-05082566 and MK-3475;
- Objective tumor response by Response Evaluation Criteria in Solid Tumors (RECIST) v1.1;
- Time-to-response (expansion cohorts only);
- Duration of response (expansion cohorts only);
- Progression-free survival (expansion cohorts only);
- **Expansion Cohorts Only:** Paired de novo tumor biopsy collection at sequential time points for analysis of exploratory mechanistic biomarkers such as IHC assessment of tumor-infiltrating lymphocytes, quantitation of T cell receptor sequences, and gene expression.

CCI

- CCI

- CCI

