3.3. DLT Definition

Severity of AEs will be graded according to CTCAE v 4.03. For the purpose of dose escalation, any of the following adverse events occurring during the DLT observation period (first 2 Cycles, ie, 6 weeks) that are attributable to one or both study drugs will be classified as DLTs:

- Hematologic:
 - Grade 4 neutropenia;
 - Febrile neutropenia, defined as absolute neutrophil count (ANC) $<1000/\text{mm}^3$ with a single temperature of >38.3 degrees C (101 degrees F) or a sustained temperature of ≥ 38 degrees C (100.4 degrees F) for more than one hour;
 - Grade ≥ 3 neutropenic infection;
 - Grade ≥ 3 thrombocytopenia with bleeding;
 - Grade 4 thrombocytopenia.
- Non-hematologic:
 - Grade ≥ 3 toxicities (non-laboratory);
 - Grade ≥ 3 nausea, vomiting or diarrhea despite maximal medical therapy;
 - Grade 4 aspartate aminotransferase (AST) and alanine aminotransferase (ALT).
- Other (non AST/ALT) non-hematologic Grade ≥ 3 laboratory value if:
 - Medical intervention is required to treat the patient, or
 - The abnormality leads to hospitalization.

- Inability to complete two infusions of MK-3475 and PF-05082566 during the DLT observation period.

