5.3. Administration

A cycle is defined as the time from Day 1 dose to the next Day 1 dose of PF-05082566. If there are no treatment delays, a cycle will be 3 weeks in duration.

All trial treatments will be administered on an outpatient basis. After Cycle 1, study drugs may be administered up to 2 days before or after the scheduled treatment day of each cycle

for administrative reasons. Patients will be observed in the clinic for at least 2 hours after each infusion of study drug.

All patients should be weighed within 72 hours prior to dosing for every cycle to ensure they did not experience either a weight loss or gain >10% from the prior weight used to calculate the amount of study drug required for dose preparation. Decision to recalculate the study drug dose based on the weight obtained at each cycle can be in accordance with institutional practice, however if the patient experienced either a weight loss or gain >10% compared to the weight used to calculate the initial dose, the amount of study drug required for preparation and administration for the current cycle must be recalculated using this most recent weight obtained.

The study drug dose escalation levels are shown in [Table 1](#). In addition, doses of PF-05082566 and MK-3475 available for dose modification according to guidelines in [Section 5.3.7](#), are shown below in [Table 7](#).

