where p_i is the prior estimate of DLT rate at dose level d_i , and $p_1 \leq p_2 \leq \dots \leq p_6$. These estimates will be projected based model sensitivity to DLTs, together with single agent safety data for both study drugs. β is an unknown single parameter modeling the dose-toxicity relationship, with prior distribution $N(0, \sigma_0^2)$, where σ_0 is the standard deviation of the normal prior distribution with mean=0. At the beginning of the trial, the initial prior value of β is set as 0, the prior mean, which gives a prior dose-toxicity model of $F_i(\beta) = p_i$ based on the power function.

In the Bayesian paradigm, the prior distribution $N(0, \sigma_0^2)$ expresses the researchers' belief in the quality of the initial estimates p_i . The smaller the standard deviation σ_0 , the more confidence researchers have in the precision of p_i . and vice versa. As the trial progresses, this prior distribution is combined mathematically with the observed data to yield the posterior distribution of the parameter β (the posterior mean of β will be calculated to model the dose-toxicity relationship). The prior distribution determines how responsive TITE-CRM is to the accumulated data. With a small σ_0 upfront, the posterior toxicity probability estimates remain close to the prior estimates unless significantly discrepant data otherwise

occur; with a large σ_0 , the model will tend to be more immediately responsive to data. In this trial, $\sigma_0=1$, which provides a reasonably flat prior distribution of β , with 90% Bayesian credible interval of $\exp(\beta) : [0.19, 5.21]$, sufficiently wide to cover a wide spectrum of dose-toxicity scenarios. Figure 3 illustrates the dose-toxicity curve (blue curve) with 90% upper and lower bounds (red curves) when the initial prior estimates p_i are (0.01, 0.04, 0.08, 0.16, 0.25, 0.35).

Figure 3. Example Plot of Prior Dose Toxicity Curve

In the TITE-CRM paradigm, patients who have enrolled in the trial but have not experienced a DLT will be included in the probability calculation with an initial weight equal to the proportion of the 6-week (2 cycles) DLT observation period the patients have completed. However the weight function will be modified if safety data suggest different weight (toxicity) patterns in Cycle 1 and Cycle 2 of PF-05082566. An adaptive cyclical weight function as proposed by Huang et al. (2014) will be implemented.

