9.6.2.2. Laboratory Test Abnormalities

The number and percentage of patients who experienced laboratory test abnormalities will be summarized according to worst toxicity grade observed for each lab assay. The analyses will summarize laboratory tests both on the entire study period and by cycle (Cycle 1, Cycle 2, and Cycles beyond 2).

For laboratory tests without CTC grade definitions, results will be categorized as normal, abnormal or not done.

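### The by-cycle adverse-event summary in Protocol 9.6.2.1 leaves Cycle 2 out of both cycle periods, unlike the laboratory split in 9.6.2.2, and the SAP neither corrects nor openly drops it

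*Protocol*

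**What the plan says.** Protocol 9.6.2.1 plans adverse-event summaries by worst toxicity grade and then fixes the periods: "The summaries will present AEs both on the entire study period and by cycle (Cycle 1 and Cycles >2".

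Protocol 9.6.2.2 fixes the periods for laboratory abnormalities differently: "The analyses will summarize laboratory tests both on the entire study period and by cycle (Cycle 1, Cycle 2, and Cycles beyond 2".

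The primary endpoint in Protocol 2.2 is "First 2 cycles Dose-Limiting Toxicity (DLT) of PF-05082566 in combination with MK-3475", and Protocol 3.3 counts "any of the following adverse events occurring during the DLT observation period (first 2 Cycles, ie, 6 weeks". Timing is a named attribute of the adverse-event secondary endpoint in Protocol 2.2 and again in SAP 3.2.1.

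SAP 5.2.7 summarizes safety endpoints over the on-treatment period unless something else is specified. SAP 6.6.1 and 6.6.1.1 then list the adverse-event tables, and none is by cycle. The version history in SAP section 1 does not mention removing a by-cycle display.

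**The concern.** Two adjacent subsections of the protocol define by-cycle periods for safety data, and only one covers every cycle. A programmer who follows 9.6.2.1 literally produces a table with a Cycle 1 column and a Cycle 3-onward column, with nowhere to put an event that starts in Cycle 2.

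Cycle 2 is not an arbitrary cycle to lose. It is the second half of the DLT window, and Protocol 9.2 names delayed-onset toxicity as a particular difficulty of combination trials. Much of what happens in Cycle 2 will not meet the DLT definition, so the DLT outputs do not replace a by-cycle view of all adverse events.

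At stake is whether the study report can show when adverse events start. Among the SAP's listed adverse-event tables, the only timing display is the infusion number at first onset of an infusion-related reaction (SAP 6.6.4). For all other adverse events, the split in Protocol 9.6.2.1 is the only planned summary by time.

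**Working it through.** No sample size, power or error rate is involved. The check is one of coverage.

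**Inputs**
- Adverse-event periods: Cycle 1; Cycles >2 (Protocol 9.6.2.1).
- Laboratory periods: Cycle 1; Cycle 2; Cycles beyond 2 (Protocol 9.6.2.2).
- Planned maximum: 32 cycles (Protocol 5.3.3).
- Cycle length: "If there are no treatment delays, a cycle will be 3 weeks in duration" (Protocol 5.3).
- DLT window: 2 cycles, 6 weeks (Protocol 3.3).

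**Coverage of cycles 1 to 32**

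| Period definition | Cycles covered | Cycles left out |
|---|---|---|
| Adverse events as written: 1; >2 | 1, 3 to 32 (31 of 32) | 2 |
| Laboratory as written: 1; 2; >2 | 1 to 32 | none |
| Adverse events if ≥2 was meant: 1; ≥2 | 1 to 32 | none |

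Under the third reading nothing is left out, but Cycle 2 is pooled with up to 32 − 2 = 30 later cycles and cannot be seen separately. Only the laboratory split shows it.

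**Share of the DLT window in time.** The window is 6 × 7 = 42 days. Without delays, Cycle 2 is 21 of them: 21/42 = 50%. This is a share of calendar time, not of events.

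**Is the strict reading of the symbol fair?** Elsewhere the protocol uses > strictly for cycles. The Schedule of Activities has a block for Cycles 3-8 followed by one for Cycles >8, and Protocol 7.5.1 and 7.5.2 sample at Cycles 1, 3, 5 and 7 and then at Cycles >7. The symbol ≥ survives in the text elsewhere, for example in Protocol 3.3.

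**Where Cycle 2 adverse events still appear**
- In the entire-study summary (Protocol 9.6.2.1).
- In the SAP's on-treatment tables and in its listings, which include all adverse events (SAP 6.6.1), with study day shown in relevant listings (SAP 5.2.4).
- If they are DLTs, in the primary-endpoint outputs: "AEs constituting DLTs will be listed by dose level" (Protocol 9.6.1), with a summary by treatment group (SAP 6.1.1.1).

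**The case against.** The strongest reply is that the sentence is not the operative table plan. Protocol section 9 and SAP section 2 both let the SAP modify the protocol's analyses, with an amendment needed only for major changes to the primary endpoint. Adverse events are a secondary endpoint. The SAP's tables use no cycle split, so no listed table has the gap. The laboratory comparison weakens in the same way, because SAP 6.6.5.1 summarizes laboratory data by nominal visit and by worst on-treatment grade, not by the three periods of Protocol 9.6.2.2.

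A second reply is that this is a one-character slip for ≥2. In that case Cycle 2 is covered and only the difference from the laboratory split remains.

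Much of this stands. The SAP may drop the display, and a slip is the likeliest explanation. But the SAP does not say that it has dropped it, so the reader is left with a protocol split that omits Cycle 2 and a SAP that has no split. The documents do not show which symbol was intended. The strict use of > for cycles elsewhere counts against reading it silently as ≥, although a symbol lost in the electronic text cannot be ruled out entirely. On either reading the table would not show Cycle 2 on its own.

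**Conclusion.** The inconsistency is real and minor. As written, one cycle of 32 falls outside the by-cycle adverse-event periods, and that cycle is the second half of the DLT window in time. The effect is limited to the timing display of a secondary safety endpoint. The conclusion rests on reading the symbol literally and on the SAP's table list being complete for adverse events.

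Three stronger readings are tempting, and the documents do not support them.

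- **That the gap affects dose finding.** Protocol 9.2 says "the weight function will be modified if safety data suggest different weight (toxicity) patterns in Cycle 1 and Cycle 2 of PF-05082566", and a reader might infer that the table informs this. No section links them. Under Protocol 3.2, DLT data go to the study statistician, who updates the model before the next patient is treated. Under Protocol 9.7, the Dose-Escalation Steering Committee reviews accumulating safety data directly. The SAP's primary analysis has a cut-off 24 months after the last patient's first dose (SAP section 2), too late to steer escalation. DLTs, weights and MTD are unaffected.
- **That half of the DLT-window events go missing.** The 50% is time. Turning it into events needs an assumed onset rate and dropout, neither of which the documents give. The events also remain in the entire-period summary and the listings.
- **That the columns fail to add up to the total.** The table counts patients by worst grade. A patient with events in several periods counts in each period but once overall, so the columns need not add up even under a complete split.

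**What to change.** 1. In Protocol 9.6.2.1, change the by-cycle periods to Cycle 1, Cycle 2, and Cycles >2, matching 9.6.2.2.
2. In SAP 6.6.1.1, add a by-cycle table of treatment-emergent and related treatment-emergent events with these three periods. For each period, the denominator is the number of patients who started that cycle (for the last period, any cycle after Cycle 2). Assign events by onset or worsening date, using the actual cycle dates already defined in SAP 6.5.3.
3. If the sponsor does not want the display, say in the SAP that the by-cycle adverse-event summary planned in the protocol is dropped, and why. That also closes the point, at the price of having no general summary of adverse-event timing.

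The cost is one phrase in the protocol and one or two tables, or one sentence, in the SAP. All the data are already collected.

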9.6.2.2. Laboratory Test Abnormalities

The number and percentage of patients who experienced laboratory test abnormalities will be summarized according to worst toxicity grade observed for each lab assay. The analyses will summarize laboratory tests both on the entire study period and by cycle (Cycle 1, Cycle 2, and Cycles beyond 2).

For laboratory tests without CTC grade definitions, results will be categorized as normal, abnormal or not done.

9.6.3. ECG

The analysis of ECG results will be based on safety analysis set patients with baseline and on-treatment ECG data. The most recent ECG collected prior to the first day of dosing will be considered the baseline ECG. ECG measurements (an average of the triplicate measurements) will be used for the statistical analysis and all data presentations. Any data obtained from ECGs repeated for safety reasons after the nominal time-points will not be averaged along with the preceding triplicates. Interval measurements from repeated ECGs will be included in the outlier analysis as individual values obtained at unscheduled time points.

QT intervals will be corrected for heart rate (QTc) using standard correction factors [ie, Fridericia's (default correction), Bazett's, and possibly a study specific factor, as appropriate]. Data will be summarized and listed for QT, HR, response rate (RR), PR, QRS, QTcF (and other correction factors, eg, QTcB as appropriate) by dose. Individual QT (all evaluated corrections) intervals will be listed by time and dose. The most appropriate correction factor will be selected and used for the following analyses of central tendency and outliers and used for the study conclusions. Descriptive statistics (n, mean, median, standard deviation, minimum, and maximum) will be used to summarize the absolute corrected QT value and changes from baseline in corrected QT after treatment, by dose and time point. For each patient and by treatment, the maximum change from baseline will be calculated as well as the maximum post-baseline value across time-points. Categorical analysis will be conducted for the maximum change from baseline in corrected QT and the maximum post-baseline QT value.

The effect of drug concentrations on corrected QT change from baseline will be explored graphically. Additional concentration-corrected QT analyses may be performed. Data may be pooled with other study results and/or explored further with PK/PD models.

Shift tables will be provided for baseline vs. worst on study QTc (one or more correction method will be used) using Maximum CTCAE Grade. As well as tables of ECG abnormality at baseline (yes, no, not done: (n, %)). Patients experiencing clinically-relevant morphological ECG changes will be summarized (including frequency and percentage).

9.7. Data Safety Monitoring Committee

An external Data Safety Monitoring Committee will not be established for this study. For the purpose of this protocol, Pfizer procedures for periodic safety review will be applied by an internal safety review team consisting of physician, safety specialist, and statistician to review individual and summary data collected in the safety and clinical databases. Procedures include:

- Surveillance for SAEs according to regulatory guidelines;
- Discussions between the Investigators and the Sponsor of AEs, laboratory test abnormalities, vital signs, and ECG findings observed at each dose level in an ongoing manner at regular teleconferences and/or meetings to determine the safety

profile and make a benefit/risk assessment and decide if further enrollment is appropriate;

- Findings having immediate implication for the management of patients on study will be communicated to all Principal Investigators in the timeframe associated with unexpected and drug-related SAEs.

During the dose-escalation phase, a Dose-Escalation Steering Committee (DESC) will be established to perform periodic review of the accumulating safety data, specifically, the DLTs. The guidance for dosing and enrollment decisions is based on the Bayesian statistical model of TITE-CRM. Other considerations may include lower grade AEs, nature and timing of the AEs, existing PK/PD data that may cause safety concerns. Following each review, the DESC will inform the study team and participating investigators on dosing and enrollment decisions. A DESC Charter will be prepared and will be available before the first DESC meeting.

10. QUALITY CONTROL AND QUALITY ASSURANCE

During study conduct, Pfizer or its agent will conduct periodic monitoring visits to ensure that the protocol and good clinical practices (GCPs) are being followed. The monitors may review source documents to confirm that the data recorded on CRFs is accurate. The investigator and institution will allow Pfizer monitors/auditors or its agents and appropriate regulatory authorities direct access to source documents to perform this verification.

The study site may be subject to review by the Institutional Review Board (IRB)/ Ethics Committee (EC), and/or to quality assurance audits performed by Pfizer, or companies working with or on behalf of Pfizer, and/or to inspection by appropriate regulatory authorities.

It is important that the investigator(s) and their relevant personnel are available during the monitoring visits and possible audits or inspections and that sufficient time is devoted to the process.

11. DATA HANDLING AND RECORD KEEPING

11.1. Case Report Forms/Electronic Data Record

As used in this protocol, the term Case Report Form (CRF) should be understood to refer to either a paper form or an electronic data record or both, depending on the data collection method used in this study.

A CRF is required and should be completed for each included patient. The completed original CRFs are the sole property of Pfizer and should not be made available in any form to third parties, except for authorized representatives of Pfizer or appropriate regulatory authorities, without written permission from Pfizer.

The investigator has ultimate responsibility for the collection and reporting of all clinical, safety and laboratory data entered on the CRFs and any other data collection forms (source

documents) and ensuring that they are accurate, authentic/original, attributable, complete, consistent, legible, timely (contemporaneous), enduring and available when required. The CRFs must be signed by the investigator or by an authorized staff member to attest that the data contained on the CRFs is true. Any corrections to entries made in the CRFs, source documents must be dated, initialed and explained (if necessary) and should not obscure the original entry”.

In most cases, the source documents are the hospital's or the physician's patient chart. In these cases data collected on the CRFs must match the data in those charts.

In some cases, the CRF, or part of the CRF, may also serve as source documents. In these cases, a document should be available at the investigator's site as well as at Pfizer and clearly identify those data that will be recorded in the CRF, and for which the CRF will stand as the source document.

11.2. Record Retention

To enable evaluations and/or audits from regulatory authorities or Pfizer, the investigator agrees to keep records, including the identity of all participating patients (sufficient information to link records, eg, CRFs and hospital records), all original signed informed consent documents, copies of all CRFs, safety reporting forms, source documents, and detailed records of treatment disposition, and adequate documentation of relevant correspondence (eg, letters, meeting minutes, telephone calls reports). The records should be retained by the investigator according to ICH, local regulations, or as specified in the Clinical Study Agreement, whichever is longer.

If the investigator becomes unable for any reason to continue to retain study records for the required period (eg, retirement, relocation), Pfizer should be prospectively notified. The study records must be transferred to a designee acceptable to Pfizer, such as another investigator, another institution, or to an independent third party arranged by Pfizer. Investigator records must be kept for a minimum of 15 years after completion or discontinuation of the study or for longer if required by applicable local regulations. The investigator must obtain Pfizer's written permission before disposing of any records, even if retention requirements have been met.

